9 STATISTICAL ANALYSIS

9.1 Sample Size and Power Analysis

All sample size estimations in this section of the protocol were undertaken using the sampsi function in Stata 11 (Statcorp LP, Texas, USA). Comparisons of groups was made assuming no continuity correction.

Little data are available on similar studies using topical oxygen therapy within randomized clinical trials making sample size estimation problematic. Large trials of dermal substitutes and negative pressure have been undertaken that can be used to indicate the potential healing in the control group. The three large trials have control healing of between 18% and 28.9% around 12 weeks after entering the trial, with a mean of 28%.^{25,27,29}

The expected improvement in healing using the active device is more problematic as there have been few comparative studies published. Aburto and Frye undertook a randomized study of 20 venous ulcers and 20 diabetic foot ulcer patients.⁴² Topical oxygen demonstrated higher healing in the DFU patients after 90 days of 90% versus 40% in the control group. Blackman et al randomized 28 patients with DFUs and obtained a similar response (82.4% versus 45.5%).²² The potential difference between treatment groups was therefore 50% and 36.9% respectively. Using these studies a total sample size of 28 and 52 would be expected based on 80% power at the 5% level of significance. Neither of these studies was blinded. It is therefore likely that the effect is likely to be substantially smaller than that experienced in these two studies.

Because of the small size of these trials and lack of blinding it has been decided to offer a more cautious approach to the calculation of sample size based on a smaller expected benefit of oxygen therapy. By combining the results of the two randomized studies already undertaken the control group achieved a healing rate of 9/21 (42.8%). In the actively treated group healing occurred in 23/27 (85.2%). Assuming an expected control rate of 43% and a difference of half that experienced in these trials of 21% (to 64%) would require a sample size of 88 patients in each group (total=176), with a power of 80% and a level of significance set at $p<0.05$.

In order to overcome the uncertainty surrounding the expected benefit, the trial will be undertaken using group sequential design (GSD) allowing for interim analysis to be performed at intervals during the trial recruitment. The interim analysis will take place after one third of subjects have been recruited, after two thirds and then a final analysis at full recruitment. The Pocock method of interim analysis will be used, which requires an equal level of significance ($p<0.022$) over the three analyses.⁴³ If the difference in primary outcome produces a probability less than this in any of the analyses then the null hypothesis is rejected and the alternative hypothesis of a difference in healing has been shown. In order to achieve this level of significance a total of 110 patients need to be recruited to each arm of the trial (total=220).

Since all patients will achieve a 12 week end point (healed versus unhealed) no uprating of this sample size will be made to take into consideration patients lost to follow up (see section 9.2).

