9.2 General Statistical Methods

Analysis Populations

Two analysis populations will be evaluated: Intent To Treat (ITT) and Per Protocol (PP). The ITT population will be considered the primary population of interest and will include all subjects who were randomized to study treatment. The PP population will include all subjects who were randomized to study treatment and had no significant protocol violations that might affect the outcome of treatment.

All participants will be followed up to the primary end point (12 weeks) irrespective of whether they were on active treatment. Participants that withdraw from treatment continue to be followed up to the 12 week end-point. Participants that die, undergo amputation or who are lost to follow up will be considered as treatment failures.

Continuous demographic variables (age, ulcer duration, etc.) will be summarized for the study population as descriptive statistics (number, mean, median, SD, minimum and maximum value), and by randomized groups. No formal inferential statistical testing will take place of baseline values in relation to randomized groups.

Categorical demographic variables, such as gender, will be summarized as a proportion of the intention-to-treat population.

All analyses will be undertaken using the STATA 11 statistical package.

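### The 110 per arm is a single-look sample size at p<0.022, not a three-look Pocock size; it gives about 83–84% power with complete outcomes, and the reason for making no loss allowance does not hold.

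*Combined protocol and SAP*

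**What the plan says.** Section 9.1 states that all sample sizes "were undertaken using the sampsi function in Stata 11", without continuity correction. The planning rates are set by "Assuming an expected control rate of 43% and a difference of half that experienced in these trials of 21% (to 64"%). The plan says that this "would require a sample size of 88 patients in each group (total=176"), "with a power of 80% and a level of significance set at" 0.05.

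The same section then introduces the group sequential design. There are analyses at one third, two thirds and full recruitment, a common Pocock level of p<0.022, and rejection of the null hypothesis if any of the three falls below that level. It concludes that "a total of 110 patients need to be recruited to each arm of the trial (total=220"), and ties this number to reaching the 0.022 level. No power is given for the 110. Section 9.6 places the interim analyses at 73 and 146 subjects.

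On losses, section 9.1 says that "no uprating of this sample size will be made to take into consideration patients lost to follow up", because every patient will be classed as healed or unhealed at 12 weeks. It refers to section 9.2, where participants who die, undergo amputation or "who are lost to follow up will be considered as treatment failures".

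**The concern.** A design that can reject at any of three looks has more power than one test at the same nominal level and the same final size. Putting the Pocock level into a one-look routine corrects for the stricter threshold but gives no credit for the two earlier chances to reject. The result is labelled as the size that the sequential design needs, and it is not.

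The second part matters more for what the trial will deliver. Coding losses as failures fills in the outcome for every patient, but it does not preserve power. It lowers both healing rates and narrows the gap between them. A reader of 9.1 would conclude that loss to follow-up costs nothing. In fact the only protection is a surplus of about 6–8 per arm that the text does not mention and that arose by accident.

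**Working it through.** **Inputs.** Healing 43% v 64%, 80% power, no continuity correction, level 0.022 at each look, looks at 73, 146 and 220, equal arms (sections 9.1 and 9.6); two-sided alternative and uncorrected chi-squared test (section 9.3); losses counted as failures (section 9.2).

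**Step 1: reproduce the plan's figures.** The single-look formula with pooled variance under the null is

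n = [z(1−α/2)·√(2p̄(1−p̄)) + z(0.80)·√(p₁(1−p₁)+p₂(1−p₂))]² / (p₂−p₁)²

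with p̄ = 0.535, √(2 × 0.535 × 0.465) = 0.7054, √(0.43 × 0.57 + 0.64 × 0.36) = 0.6896, z(0.80) = 0.8416 and 0.21² = 0.0441.

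- α = 0.05: (1.9600 × 0.7054 + 0.8416 × 0.6896)² / 0.0441 = 87.4, so 88. This matches the plan.
- α = 0.022: (2.2904 × 0.7054 + 0.8416 × 0.6896)² / 0.0441 = 109.3, so 110. This matches the plan.

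Variants at 0.022 do not match: one-sided 91, continuity-corrected 119, unpooled variance 106. The 110 is therefore a one-look answer that carries 80% power over from the previous step.

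**Step 2: size for three looks.** The joint normal distribution of the test statistic at information 1/3, 2/3 and 1 gives a Pocock critical value of 2.289 (nominal level 0.02205). The inflation over a fixed design at 80% power is 1.166. Then 1.166 × 87.4 = 101.9, so 102 per arm. Direct calculation with the pooled-variance test gives 79.8% at 102 and 80.2% at 103. Simulating the chi-squared test gives about 79% at 102, 80% at 103 and 81% at 104. The 80% size is thus about 102–104 per arm.

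**Step 3: power of 110 per arm with three looks.** Pooled-variance normal theory gives 82.9%. Simulation of the planned test (1,000,000 trials; 37/36, 73/73 and 110/110 per arm) gives cumulative power of 29.6%, 64.5% and 84.3%. Normal theory with unpooled variance gives 84.2%, but that is not the variance behind the plan's 109.3 or its chi-squared test, so it does not independently confirm the simulation. A fair statement is 83–84%.

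**Step 4: type I error.** Three equally spaced looks at 0.022 give an overall two-sided level of 0.0499 by normal theory. Simulation with a 43% healing rate in both arms gives about 5.2%, the excess being due to the discreteness of binomial counts.

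**Step 5: losses counted as failures.** The plan gives no loss rate, so the rates L below are assumptions. Loss is taken as equal in the two arms and unrelated to healing, so the rates become 0.43(1−L) and 0.64(1−L) and the difference becomes 0.21(1−L).

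| Loss L | Rates | Difference | Power, pooled normal | Power, simulated |
|---|---|---|---|---|
| 0% | 43.0% v 64.0% | 21.0 points | 82.9% | 84.3% |
| 5% | 40.9% v 60.8% | 20.0 points | 78.4% | 80.2% |
| 10% | 38.7% v 57.6% | 18.9 points | 73.7% | 75.5% |
| 15% | 36.6% v 54.4% | 17.9 points | 68.7% | 70.5% |

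Pooled normal theory crosses 80% between 3% and 3.5% loss; the simulation reaches it at about 5%.

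**The case against.** The strongest reply is that nothing harmful follows with complete data. Power is at least 80% under the plan's own rates, overall alpha is close to 5%, and the synopsis itself describes 220 as a conservative estimate. No boundary, look or decision changes. This stands. A reader might infer from a wrong derivation that the trial is undersized or that its error rate is inflated by the method; the figures above show neither.

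A reader might also infer that the plan states a wrong power for the 110. It does not. The 80% is attached to the 88 per group, and the step to 110 mentions only the significance level. That 110 was meant to carry 80% is an inference. It is a strong one, because the 80% formula returns 110 exactly, but the fault is a missing power figure and a mislabelled derivation, not a false power claim.

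On losses, three limits are fair. The rates are assumed. The calculation treats 43% and 64% as rates among patients with known outcomes; section 9.1 does not say how losses were handled in the two source studies, and if those rates already count losses as failures the dilution is smaller. And section 9.5 says that subjects with missing data are omitted from the relevant analyses. Under omission, about 5% loss (105 per arm) leaves simulated power near 81%, and about 10% (99 per arm) near 78%, so the drop depends on the rule. Section 9.2 is the rule that 9.1 relies on, however, and under either rule loss reduces power. The plan does provide for following withdrawn subjects to 12 weeks, which should limit loss, but section 8.2.6 accepts that some will decline the visit and section 8.2.12 defines when a subject is lost.

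**Conclusion.** The point holds as a correction to section 9.1. The 110 per arm is a fixed-sample size at two-sided 0.022 with 80% power. The three-look design needs about 102–104 per arm for 80%, so the stated figure is 6–8 per arm higher than required, and 110 per arm gives about 83–84% with complete outcomes. This rests on 43% v 64%, equal allocation, and looks based on 73 and 146 subjects with 12-week outcomes.

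The justification for making no loss allowance does not hold. Under failure coding, with loss equal in both arms and unrelated to healing, power at 110 per arm is about 78–80% at 5% loss, 74–76% at 10% and about 70% at 15%. The surplus keeps 80% power only up to roughly 3–5% loss, the exact point depending on the method of calculation. This is not evidence that the trial will be underpowered, because the plan gives no expected loss rate.

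**What to change.** Keep 220. In section 9.1:

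- Replace the sentence that presents 110 as the size needed with: 110 per arm, with three equally spaced Pocock looks at two-sided 0.022, gives about 83–84% power for 43% v 64% with complete outcomes; 80% power would need about 102–104 per arm.
- Replace the no-uprating justification with: counting deaths, amputations and losses as failures dilutes the difference, and the surplus over the 80% size keeps 80% power only up to roughly 3–5% loss. Show the assumed loss rates with the resulting power, say that loss is taken as equal in both arms and unrelated to healing, and name section 9.2 as the rule applied.

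The cost is a change of wording in 9.1. No patients are added, and the boundaries and the timing of the looks do not change.

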9.2 General Statistical Methods

Analysis Populations

Two analysis populations will be evaluated: Intent To Treat (ITT) and Per Protocol (PP). The ITT population will be considered the primary population of interest and will include all subjects who were randomized to study treatment. The PP population will include all subjects who were randomized to study treatment and had no significant protocol violations that might affect the outcome of treatment.

All participants will be followed up to the primary end point (12 weeks) irrespective of whether they were on active treatment. Participants that withdraw from treatment continue to be followed up to the 12 week end-point. Participants that die, undergo amputation or who are lost to follow up will be considered as treatment failures.

Continuous demographic variables (age, ulcer duration, etc.) will be summarized for the study population as descriptive statistics (number, mean, median, SD, minimum and maximum value), and by randomized groups. No formal inferential statistical testing will take place of baseline values in relation to randomized groups.

Categorical demographic variables, such as gender, will be summarized as a proportion of the intention-to-treat population.

All analyses will be undertaken using the STATA 11 statistical package.

9.3 Primary outcome analysis

The primary endpoint is the “Incidence of complete wound closure within 12 weeks”.

The null hypothesis to be tested is that there is no difference between treatment groups in terms of the rate of wound healing after 12 weeks of study treatment. The alternative hypothesis is that such a difference exists.

Uncorrected Chi squared analyses will be used to determine the difference between treatment groups in terms of wound closure rate within 12 weeks, at the interim analysis. 95% confidence intervals will be estimated using the normal approximation interval.

Logistic regression analysis will be used to determine the effects of confounding on the primary outcome at the trial end. In particular, gender, age, ulcer duration, size and diabetic factors will be considered in the model. A stepwise procedure will be used to eliminate non-significant covariates from the model. The effect of different centers' outcomes will be entered as a random effect into the model.

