7. ASSESSED VARIABLES

7.1. Efficacy Assessment

7.1.1. Primary Efficacy Assessment

The primary endpoint is the “Incidence of complete wound closure within 12 weeks”.

Only one ulcer (the index ulcer) will be assessed per subject. In subjects with multiple ulcers, this will be the largest ulcer present fulfilling all other inclusion criteria.

Closure is defined as skin re-epithelialization without drainage or dressing requirements which is confirmed at 2 consecutive trial visits 2 weeks apart.²³

Wound closure checks will be performed weekly. The closure of the wound is a clinical judgment by the investigator. A digital picture reviewed by the central assessor will also provide evidence of wound closure.

Ulcers will be measured by the central assessor. A deidentified digital photograph of the ulcer will be taken with and transmitted by the study sites using a wifi/wireless enabled tablet device. The ulcer's surface area, circumference, maximum and minimum diameters will be recorded at baseline assessment of the subject.

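### Both interim stopping tests ignore baseline ulcer area and duration, which are already collected, and section 9.3 does not say which test faces 0.022 at the final look.

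*Combined protocol and SAP*

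**What the plan says.** The primary endpoint is binary: "Incidence of complete wound closure within 12 weeks". Section 9.1 sizes the trial as an unadjusted comparison of two proportions (43% against 64%) and notes that "Comparisons of groups was made assuming no continuity correction". It adopts a Pocock boundary of p<0.022 at each of three analyses and concludes that "In order to achieve this level of significance a total of 110 patients need to be recruited to each arm of the trial". Crossing the boundary at any one look rejects the null. Section 9.6 places the interim looks at 73 and 146 subjects.

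Section 9.3 then describes two analyses. First, "Uncorrected Chi squared analyses will be used to determine the difference between treatment groups"; the same sentence goes on to limit this to the interim analysis. Second, "Logistic regression analysis will be used to determine the effects of confounding on the primary outcome at the trial end". That model considers gender, age, ulcer duration, size and diabetic factors, removes non-significant covariates stepwise, and carries center as a random effect.

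On the data available, section 7.1.1 says "The ulcer's surface area, circumference, maximum and minimum diameters will be recorded at baseline assessment of the subject", with measurement by the central assessor. Wound history, including duration, is in the section 8.1.1 schedule. Eligibility (section 3.1) allows 1 to 20 cm² and 4 weeks to 1 year. Section 5 randomizes by permuted blocks and mentions no stratification by area or duration.

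**The concern.** Closure must happen inside a fixed 12 weeks, and eligible ulcers differ 20-fold in area. The plan's own healing measure in section 9.4.2 is a linear advance of the wound edge. On that scale, if ulcers are taken as round, a 20 cm² ulcer has √20 ≈ 4.5 times the radius of a 1 cm² ulcer and needs 4.5 times as long to close at the same edge speed. Section 9.3 itself lists size and duration as covariates for the primary outcome.

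Yet at 73 subjects, about 36 per arm, nothing in the design or the test balances or adjusts for them. A trial-end model cannot undo a rejection already declared at an interim look. At the final look the plan describes a different kind of analysis and does not say whether it replaces the chi-square as the test held to 0.022. At stake are some efficiency, the robustness of individual early decisions, and a clear definition of the third test.

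**Working it through.** **1. The plan's sample size.** Inputs from section 9.1: p₀ = 0.43, p₁ = 0.64, d = 0.21, power 80%, no continuity correction. The formula is

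n = [z_α/2·√(2p̄q̄) + z_β·√(p₀q₀ + p₁q₁)]² / d²,

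with p̄ = 0.535, √(2p̄q̄) = 0.7054 and √(0.2451 + 0.2304) = 0.6896.

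- Two-sided 0.05: (1.960×0.7054 + 0.8416×0.6896)² / 0.0441 = 87.4, so 88 per arm.
- Two-sided 0.022: (2.290×0.7054 + 0.8416×0.6896)² / 0.0441 = 109.3, so 110 per arm.

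Both match the plan.

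**2. Power and alpha of the unadjusted design.** Single-look power is Φ[(0.21√n − 2.290×0.7054)/0.6896].

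- n = 36.5 per arm: 30.7%
- n = 73 per arm: 60.2%
- n = 110 per arm: 80.3%

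Over three equally spaced looks at 0.022, overall alpha is 0.0498 and overall power about 84%. If the planned effect is real, the trial stops by the second look in about 65% of runs. So 65/84 ≈ 77% of positive results would rest on the unadjusted interim test.

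**3. What adjustment could add.** The documents give no prognostic strength, so it is assumed: one standard-normal baseline score with an odds ratio (OR) per SD from 1.0 to 4.1. Marginal rates were held at 43% and 64%, looks were at 73/146/220, and permuted blocks of 4 were assumed. The uncorrected chi-square was compared with a covariate-adjusted logistic score test in 4,000 runs under the alternative (SE about 0.6 points) and 6,000 under the null (SE about 0.3 points).

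| OR per SD | Three-look power, chi-square | Three-look power, adjusted | Look-1 rejection, chi-square / adjusted | Overall type I error, chi-square / adjusted |
|---|---|---|---|---|
| 1.0 | 84.8% | 84.0% | 29.7 / 30.9% | 5.7 / 5.8% |
| 1.5 | 83.9% | 84.3% | 29.4 / 32.9% | 4.8 / 5.1% |
| 2.0 | 84.9% | 87.2% | 30.2 / 35.4% | 5.7 / 5.7% |
| 2.7 | 83.6% | 89.3% | 29.0 / 37.6% | 5.0 / 5.1% |
| 4.1 | 84.0% | 92.2% | 29.0 / 43.0% | 5.5 / 5.4% |

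The gain runs from nil, within simulation error, to about 8 points. A separate simulation with two fixed covariates gave about 0, 3 and 5 points at ORs of 1.5, 2.0 and 2.7.

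**4. Chance imbalance at 73 subjects.** The between-arm difference in a standardised baseline score has SE √(2/36.5) = 0.234. An imbalance above 0.3 SD favouring the active arm therefore has probability P(Z > 0.3/0.234 = 1.28) ≈ 10%. Given that imbalance and a real effect, the chi-square's chance of stopping at look 1 moves from about 30% to 37%, 47% and 59% at ORs of 1.5, 2.0 and 2.7. Adjusted and unadjusted look-1 decisions differ in 6% to 14% of trials over that range when the effect is real, and in 1% to 2% under the null.

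**5. Error rate of the proposed test.** With two fixed covariates, overall null error was 4.7% for the chi-square, 5.3% for a likelihood-ratio test and 5.0% for the score test. In another run with three covariates, the likelihood-ratio version reached 5.8% overall (chi-square 5.1%) and 3.0% false stops at look 1 (chi-square 2.1%). This is why the score test and no more than two covariates are preferred.

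**The case against.** An unadjusted test with correct alpha and the planned power is a conventional choice. That stands. A reader might infer that planned power is being lost, but steps 1 and 2 show that the chi-square delivers what section 9.1 promised.

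A reader might also infer that all three looks rest on the chi-square. The sentence in section 9.3 names the interim analysis only, and the trial-end model does consider size and duration. For the third look, the defect is the unstated choice of test.

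The stepwise rule is less harmful than it looks. If a covariate correlates 0.3 with closure, Fisher's z gives atanh(0.3)·√217 = 4.56 against a cut-off of 1.96, so it is significant at 0.05 in about 99.5% of trials of 220. A covariate strong enough to bring the gain would normally be kept. But retention is still decided by the data, and this does nothing for the interim looks.

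Chance imbalance is symmetric and already inside the test's error rate, so it does not inflate false positives. Crossing the boundary at look 1 needs an observed difference of about 2.290×0.1168 = 27 points, more than the planned 21. What remains is that individual early decisions depend partly on how ulcer sizes happened to fall.

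Finally, the gain rests on a prognostic strength that the documents do not give. At an OR of 1.5 per SD or less there is essentially none.

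**Conclusion.** The point holds as a missed efficiency and an unclear final test. It is not an error in the sample size or in alpha. Both interim decisions use a test that ignores collected and plausibly prognostic baseline data. At trial end those data have no assured place, and the analysis held to 0.022 is not named.

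The forgone gain is about 0 to 8 points of three-look power for an assumed OR of 1.0 to 4.1 per SD. It also includes protection of look-1 decisions, 6% to 14% of which would differ at ORs of 1.5 to 2.7 if the effect is real. These figures assume a single normally distributed score and no center effect. Larger gains could be claimed by taking one strong correlation as a default, but nothing in the documents fixes such a value. N need not rise. The change is worth making before the first interim because it costs little and also settles which test is used at the third look.

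**What to change.** In section 9.3, name one test for all three looks: the treatment effect from a logistic model with log baseline ulcer area and log ulcer duration specified in advance and kept regardless of significance. Drop the stepwise step from this analysis. Compare the score-test p-value with 0.022. Report the marginal (standardised) risk difference with its interval, and keep the uncorrected chi-square at each look as a sensitivity analysis. State also where the random center effect belongs, since the simulations above did not include one.

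If the sponsor prefers to keep the chi-square as the decisive test, the minimum change is to say that it applies at the final look too, with a fixed-covariate model in support. That removes the ambiguity but not the loss of efficiency.

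The cost is SAP wording and a few lines of Stata, with no new data or subjects. There are three small downsides. Baseline area and duration must be clean before each interim cut. A likelihood-ratio version of the test would be slightly anti-conservative at 73 subjects. The gain is nil if the covariates turn out to be weak.

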9.6 Independent Data Monitoring Committee

As suggested by international guidelines on data monitoring committees, an independent Data Monitoring Committee (DMC) will be formed to decide whether the predefined criteria for early stopping of the trial are met.^{46,47} The DMC will meet at the interim analysis to be performed after 73 and 146 subjects and at the end of study. In the event of new unanticipated and related adverse effects being reported, the DMC will convene for an unscheduled meeting and will determine at that time the need for additional review and or action.

The Data Monitoring Committee will consist of three to five independent experts outside of the study group. These members:

- will not be involved in the conduct of the clinical trial
- will not have any financial interest in the outcome of the study
- will have no planned authorship in publications on study results
- will not serve in parallel on the DMC of a clinical trial with diabetic patients with a different sponsor

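### The 95% interval planned in 9.3 does not match the p<0.022 rule over three looks, so it can exclude zero when the planned test has not rejected

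*Combined protocol and SAP*

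**What the plan says.** Section 9.1 uses the Pocock method, "which requires an equal level of significance ($p<0.022$) over the three analyses". The looks come at one third, two thirds and full recruitment, and the rule covers all three: "If the difference in primary outcome produces a probability less than this in any of the analyses then the null hypothesis is rejected". Section 9.6 gives the interim sizes: "The DMC will meet at the interim analysis to be performed after 73 and 146 subjects and at the end of study". The total is 220, or 110 per arm.

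Section 9.3 names the test: "Uncorrected Chi squared analyses will be used to determine the difference between treatment groups in terms of wound closure rate within 12 weeks", which the same sentence ties to the interim analysis. The next sentence is the only statement about intervals for the primary endpoint: "95% confidence intervals will be estimated using the normal approximation interval". It does not say what the interval estimates or at which analyses it is given. For the end of the trial, 9.3 adds a logistic regression for confounding and names no other interval.

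Nowhere do the documents match the interval's level to 0.022, adjust the interval or the estimate for the sequential design, or say how to read the interval when p is between 0.022 and 0.05.

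**The concern.** The test uses a multiplier of 2.29 and the interval 1.96, so a band of results gives two different messages. At an interim look, the DMC would see an interval excluding zero beside a rule that says continue. Section 8.2.11 also allows termination if interim data show no clear benefit, without a numerical criterion, so the reading of an interim interval could carry weight. At the final look, a trial that has not shown a difference could be published with an interval that excludes zero.

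Two further effects follow from repeated looks. The interval's coverage at the look where the trial stops is below its stated 95%. After an early stop for a large difference, the plain estimate and its interval also sit too high.

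**Working it through.** **Inputs**

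- Level 0.022 at each of three looks, rejection at any one (9.1).
- Looks at 73, 146 (9.6) and 220 subjects (9.1). I take 37 active/36 control, 73/73 and 110/110, counting subjects whose 12-week outcome is known. The 37/36 split is my assumption.
- Control closure 43%, difference 21 points (9.1). As a second case, control 28%, the mean that 9.1 quotes from three large trials. Differences of 10.5 and 15 points are smaller effects of my choosing.
- Uncorrected chi-squared test (pooled variance) and normal-approximation interval (unpooled variance) (9.3).

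**1. The plan's own figures reproduce.** The Pocock constant for three equally spaced looks is 2.289, a nominal p of 0.0221. Sample size per arm is

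n = [z√(2p̄q̄) + 0.842√(p₁q₁ + p₂q₂)]² / δ², with p̄ = 0.535, δ = 0.21.

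- z = 1.960: (1.960×0.7054 + 0.842×0.6896)² / 0.0441 = 87.4, so 88.
- z = 2.290: (2.290×0.7054 + 0.842×0.6896)² / 0.0441 = 109.3, so 110.

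Overall type I error at 0.022 per look is 4.99% by normal theory. By exact binomial enumeration it is 5.1% at either control rate.

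**2. Multipliers.** The interval matching p<0.022 is 97.8%, with z(0.989) = 2.290. The plan uses 1.960. Ratio: 2.290/1.960 = 1.17.

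**3. Two examples**

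- *Final look, 64/110 versus 48/110.* Difference 14.5 points. Pooled rate 112/220 = 0.509, SE 0.0674, z = 2.158, p = 0.031: no rejection. Unpooled SE 0.0667, so the 95% interval is 14.5 ± 1.960×6.67 = 1.5 to 27.6. The 97.8% score interval is -0.9 to 29.3.
- *Look 1, 25/37 versus 15/36.* Difference 25.9 points. Pooled rate 40/73 = 0.548, SE 0.1165, z = 2.223, p = 0.026: continue. Unpooled SE 0.1126, so the 95% interval is 25.9 ± 1.960×11.26 = 3.8 to 48.0.

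**4. How often.** Exact enumeration over the three looks; the interim row comes from 1,000,000 simulated trials. Control rate 43%, with 28% in brackets.

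| Share of all trials | No effect | 15 points | 21 points |
|---|---|---|---|
| Final look reached, test not significant, 95% interval excludes zero | 1.9% [2.4%] | 8.4% [11.0%] | 4.9% [5.6%] |
| At least one interim look that continues although its 95% interval excludes zero | 6% [6%] | 23% [22%] | 26% [24%] |

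Coverage of the 95% interval at the stopping look is 92.9% [92.6%] with no effect, 93.2% [93.1%] with 10.5 points and 93.8% [94.2%] with 21 points. With no effect, the interval at the stopping look excludes zero in 7.1% [7.4%] of trials, against about 5% for the test.

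**5. Estimate after stopping.** With a 43% control rate and a true 21 points, 30% of trials stop at look 1 with a mean estimate of 34 points. Over all trials the mean is 24.

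**6. Which interval removes the conflict.** Widening the normal-approximation interval to 97.8% is not quite enough at look 1, because the test pools the variance and the interval does not. For 25/37 versus 15/36 it gives 0.1 to 51.7, still excluding zero. The 97.8% score interval, which inverts the test, gives -0.8 to 49.2. With the 97.8% normal-approximation interval, this look-1 disagreement occurs in 1.3% of trials with no effect and about 8% with 21 points at 43% control (0.4% and 4.2% at 28%). With the score interval it is zero by construction.

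For 64/110 versus 48/110, stage-wise ordering with boundary 2.29 and Z = 2.158 at look 3 gives two-sided p = 0.057, a median-unbiased estimate of 13.7 points and a 95% interval of -0.4 to 27.1. This agrees with the non-rejection.

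**The case against.** **The sentence may not mean the difference.** Sections 9.4.2 and 9.4.4 say explicitly that their intervals are for the difference, and 9.3 does not. If it meant an interval for each arm's closure rate, there would be no zero to exclude. But the sentence follows directly on a test of "the difference between treatment groups in terms of wound closure rate within 12 weeks, at the interim analysis", and 9.4.4 uses the same normal-approximation wording for a difference. The reading is the natural one, though it remains a reading.

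**The final chi-squared test is inferred too.** Section 9.3 ties it to the interim analysis and mentions only logistic regression at trial end. However, 9.1 applies 0.022 to all three analyses and sizes the trial by an uncorrected comparison of two proportions. I take that as the deciding test at the end; the final-look figures depend on it.

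**No decision rests on the interval.** This stands. The p-value rule alone decides efficacy and controls type I error. The 23% and 26% interim figures are trials with a real effect that continue as designed.

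**The coverage loss is small.** This also stands. Without interim looks, the same interval at 43% versus 64% covers 94.4%, 94.9% and 94.7% with 36, 73 and 110 per arm. At the design effect, repeated looks therefore cost about 1 point; with no effect, about 1.5 to 2 points.

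**The remedy offers more than a matching level.** Other valid methods exist, and bias after early stopping is common to sequential designs. But matching the level alone leaves the look-1 disagreement and the bias, both of which the plan can address in advance.

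**Conclusion.** The concern holds. Followed as written, the plan reports an interval that can contradict its own test and whose coverage at stopping is 92.6% to 94.2% in the cases examined. A non-significant final result with an interval excluding zero occurs in 1.9% to 11.0% of trials. An interim look that continues beside such an interval occurs in 6% to 26%. After an early stop, the plain estimate is also too high.

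This is a fault of reporting and interpretation; the decision rule keeps its 5% level. It should be corrected before any comparative look. The conclusion rests on reading the 9.3 interval as one for the difference in closure proportions, given at all three analyses, with the uncorrected chi-squared test deciding at each. The frequencies also depend on the assumed look-1 split and closure rates.

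**What to change.** Replace the interval sentence in 9.3 with:

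> At each analysis, including the final, the difference in 12-week closure proportions will be reported with a 97.8% score interval that inverts the uncorrected chi-squared test, matching the p<0.022 rule. When the trial stops, a median-unbiased estimate and 95% interval by stage-wise ordering will also be reported.

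This wording treats the chi-squared test as decisive at the final look as well, which 9.3 should state outright.

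Sample size and the p<0.022 rule stay the same. The 97.8% interval is about 17% wider than the planned one. In the 64 versus 48 example, the stage-wise 95% interval is about 5% wider (27.5 against 26.1 points), with the estimate at 13.7 instead of 14.5. The score interval takes a few lines of code. The stage-wise interval needs a short numerical-integration routine, which the SAP should name, since 9.2 commits all analyses to STATA 11.
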